Specific Aim 2: Conduct a pilot RCT comparing CBTi-CB (n=30) to SE (n=30) delivered remotely to (a) assess the acceptability and feasibility of RCT procedures; (b) determine the distribution and variability of the primary outcomes (insomnia severity, health-related functioning); and (c) assess potential mechanisms of change (sleep-related behaviors; sleep-related beliefs; sleep self-efficacy; and cannabis use motivation) within the CBTi-CB and SE conditions.

The proposed project addresses a key objective articulated in the most recent **NIDA Strategic Plan**, specifically, to “develop and test novel treatments based on the science of addiction” (Objective 3.1). This work is significant because of the large and growing number of US adults who use cannabis to manage their insomnia. Given the extent of daily cannabis use in users of cannabis for insomnia, intervening on sleep in this group represents the opportunity to engage and improve outcomes in those with heavy cannabis use. The study is innovative because it targets insomnia, a highly comorbid condition in a group of non-treatment seeking individuals, and proposes that improvement in sleep will reduce cannabis use and improve health-related functioning. The impact is enhanced by leveraging telemedicine approaches to optimize reach of the treatment.

RESEARCH DESIGN AND METHODS

Overview of approach. The purpose of this project is to adapt, iteratively refine, and pilot test an existing CBTi intervention for use in adults who currently use cannabis for insomnia (CBTi-CB). The proposed work is consistent with Stages IA/IB of the NIH Stage Model of Intervention Development.^{20,21} Also in line with these recommendations, the pilot trial will gather data on the extent to which participation in the CBTi-CB intervention is associated with changes in the proposed mechanisms of action of the intervention.^{20,21} The proposed project has two primary aims: (1) adapt and iteratively refine remotely-delivered CBTi-CB to address the unique needs of individuals using cannabis for insomnia and develop and refine a matched remotely-delivered Sleep Education Control (SE) condition; and (2) conduct a pilot randomized controlled trial (RCT) comparing remotely-delivered CBTi-CB to SE to (a) assess the feasibility of RCT procedures; (b) determine the distribution and variability of the primary outcomes (insomnia severity, health-related functioning); and (c) assess potential mechanisms of change.

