The primary outcomes of interest include insomnia severity, functioning, and frequency of cannabis use. Potential mechanisms of the intervention include sleep-related behaviors (e.g., changes in time in bed, regularity of sleep schedules) and sleep-related cognitive factors (e.g., changes in sleep-related beliefs, self-efficacy to manage sleep without cannabis, motivation to use cannabis to manage sleep). Based on recent guidelines for Stage 1B research, we will calculate means and standard deviations for primary and mechanistic measures at baseline, post-treatment, and follow-up, as well as change scores for the CBTi-CB and SE groups. In line with recent recommendations for analysis of data from pilot studies, we will focus on estimation of confidence intervals for between-group differences at baseline and all follow-ups.

Moreover, although we recognize that the proposed project will not have adequate power to serve as a definitive study of intervention effects, to prepare for analyses for the future large-scale definitive trial we will compare the outcomes between the two study groups. We hypothesize that intervention participants will have less severe insomnia, better functioning, and lower frequency of cannabis use at follow-ups. The primary outcomes are hypothesized to meet the assumptions of continuous variables, and we will consequently use t-tests to make comparisons. If, however, the distribution of a measure is skewed, alternative modeling strategies (e.g., Poisson regression) will be used. We will examine separate models by sex (i.e., stratified analyses). We will also conduct exploratory analyses of how potential mediators (e.g., self-efficacy) relate to changes in insomnia and cannabis use, and will examine whether changes in insomnia and cannabis use are correlated. Although our sample size is not sufficient to conduct formal mediation analysis, results will inform the identification of those variables that best capture the mechanisms for intervention effects. We will use an intent-to-treat framework.

HUMAN SUBJECTS CONSIDERATIONS

For all phases of this study, approval will be obtained from the Institutional Review Board at the University of Michigan. This research is also covered by a Certificate of Confidentiality from NIDA.

Specific Aim 1-Phase 1: Qualitative Interviews

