Follow-up assessments will be conducted in person in the community or in our offices at the University of Michigan, or via emails containing REDCap survey links or mailed paper surveys where participants can complete surveys on their own. For those assessments that occur in the community, research staff will arrange to meet participants at a convenient and confidential location in the community (e.g., a local library, their home). If we interview a participant in his/her home, we will arrange for a second research staff member to go along for staff safety reasons. We have used this process successfully in our prior work with adults with SUD.

Data Collection: Assessment content will measure demographic characteristics, reasons for seeking cannabis and current uses (must include insomnia), frequency and severity of insomnia, and presence of co-occurring exclusionary medical/psychiatric conditions, and other sleep disorders. The screening assessment will include questions that will allow for determination of eligibility. Baseline assessments are intended to confirm eligibility and assess the acceptability of the measures used that will obtain greater detail about sleep, functioning, substance use and the proposed mechanisms of change in our theoretical model in our next phase. Data will be collected via emailed surveys, tablets, paper, actigraphy, and urine drug screens.

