Modified Marijuana Motives Questionnaire (MMQ)		X			
Medical Marijuana Use		X			
Prescription Misuse (BOYD)		X		X	X
Side Effect Checklist (SECL)		X		X	X
Marijuana withdrawal checklist revised (MWC-R)		X		X	X
PEG Three-item Scale Assessing Pain Intensity and Interference		X		X	X
BRFSS Model 16(Marijuana Use Type)		X		X	X
Multidimensional Fatigue Inventory (MFI-20)		X		X	X
Epworth Sleepiness Scale		X		X	X
Therapy Evaluation Questionnaire		X		X	
Working Alliance Inventory-SR				X	
Daily Sleep/Wake Diary		X	X	X	X
Actigraphy		X		X	X
Session Attendance			X	X	

Primary outcomes: The ultimate goal is to use this pilot study to provide all of the necessary elements to conduct a future fully-powered RCT comparing these two conditions. We hope to assess the acceptability and feasibility of RCT procedures to determine the distribution and variability of the primary outcomes (insomnia

severity). This will be measured by the change from baseline Insomnia Severity Index score to the score at study completion.

All remuneration for the study will be in the form of gift cards or cash. Participants will be remunerated with a \$40 for the completion of baseline assessment, \$40 for completion of each follow-up assessment, \$20 for completing four out of seven days of the daily online survey for every week before the first follow up and \$10 for completing four out of seven days of the daily online survey for the week before the 2nd follow up, plus an additional \$10 incentive for a urine drug screen at both follow ups. Participants will also receive \$30 to compensate them for any potential charges related to the use of their technology. Participants who do not complete all therapy sessions will still receive the \$30 to cover technology costs, however, they must have completed at least one phone session.

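### Cannabis-use motivation is a named mechanism of change, but the only motives questionnaire is scheduled at baseline alone and no repeated measure is named for it

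*Combined protocol and SAP*

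**What the plan says.** Specific Aim 2(c), under Objectives, commits the pilot to "assess potential mechanisms of change (sleep-related behaviors; sleep-related beliefs; sleep self-efficacy; and cannabis use motivation) within the CBTi-CB and SE conditions". The Overview of approach says that "the pilot trial will gather data on the extent to which participation in the CBTi-CB intervention is associated with changes in the proposed mechanisms".

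The Aim 2 Data Analysis section narrows the construct to "motivation to use cannabis to manage sleep" and lists it among cognitive factors expected to change. It then states that "we will calculate means and standard deviations for primary and mechanistic measures at baseline, post-treatment, and follow-up, as well as change scores" for each arm, and that "we will focus on estimation of confidence intervals for between-group differences at baseline and all follow-ups". It plans exploratory analyses of how potential mediators relate to change in insomnia and cannabis use, and says that "results will inform the identification of those variables that best capture the mechanisms for intervention effects".

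The RCT Assessment Instruments table (Human Subjects Considerations, Specific Aim 2) has columns for screening, baseline, before and/or after session, about 8 weeks and about 16 weeks. The row beginning "Modified Marijuana Motives Questionnaire (MMQ" carries one mark, under Baseline. The beta-testing table under Specific Aim 1, Phase 2 schedules it the same way. The text before that table says the beta-phase baseline tests the acceptability of measures that will give greater detail on, among other things, "substance use and the proposed mechanisms of change in our theoretical model in our next phase". Nowhere does the document say which instrument measures which mechanism.

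**The concern.** A mechanism of change needs at least one measurement after randomization. The MMQ is the only instrument whose title refers to motives, and its schedule provides none. If it is the intended measure, the change scores, the follow-up intervals and the relation of motivation to change in insomnia and cannabis use cannot be produced.

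If a different, repeated instrument was intended, the data will exist. But the choice of instrument and score then stays open until someone can see the results, which weakens the evidence about which mechanisms to carry into the full trial.

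The construct is not peripheral. The CBTi-CB description treats cannabis use as a poor way of coping with insomnia that therapy should replace with other strategies. Motivation to use cannabis for sleep is therefore close to the theory the pilot is meant to inform.

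**Working it through.** The plan gives no figure to reproduce. The check sets the planned analyses against the rows of the RCT table.

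**Mechanism against schedule.** The document assigns no instruments, so the match below is by title and, for sleep behaviors, by the examples in Data Analysis (time in bed, regularity of schedule).

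| Mechanism in Aim 2(c) | Instrument matching by title or example | Baseline | ~8 weeks | ~16 weeks |
|---|---|---|---|---|
| Sleep-related behaviors | Sleep/wake diary, actigraphy | yes | yes | yes |
| Sleep-related beliefs | DBAS-16 | yes | yes | yes |
| Sleep self-efficacy | Modified Self Efficacy Scale | yes | yes | yes |
| Cannabis-use motivation | MMQ | yes | no | no |

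Motivation is the only one of the four without a title-matched instrument repeated at follow-up.

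**What the MMQ can deliver as scheduled**
- Means and SDs: 1 of 3 time points.
- Change scores per arm (baseline to ~8 weeks, baseline to ~16 weeks): 0 of 2.
- Between-group confidence intervals: baseline only, so 1 of 3 overall and 0 of 2 at follow-up.
- Follow-up forms not collected: 60 participants x 2 follow-ups = 120 at most, before attrition.

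**How unusual this is in the table.** Nineteen rows are marked at Baseline. Fifteen are repeated at both follow-ups: PHQ-8, SF-12, Timeline Follow Back, self-efficacy, DBAS-16, Substance Use Sleep Scale, prescription misuse, side effects, withdrawal, PEG, BRFSS, fatigue, Epworth, diary and actigraphy. One is repeated at ~8 weeks only (Therapy Evaluation Questionnaire). Three are repeated at neither: Morningness/Eveningness, MMQ and Medical Marijuana Use. Check: 15 + 1 + 3 = 19.

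**Could this be a fault in the text extraction?** It is unlikely. Neighbouring rows keep their follow-up marks, and the separate beta-testing table also shows the MMQ at baseline only.

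**Could another instrument fill the gap?**
- The Substance Use Sleep Scale (baseline, ~8, ~16 weeks) and Perceived Relief (screening, ~8, ~16 weeks) are repeated. Their content is not described and neither is linked to motivation.
- The Cannabis Expectancy Questionnaire was repeated in the beta-testing table but is absent from the RCT table.
- Timeline Follow Back records use, not motivation.

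The number of repeated instruments designated for motivation is therefore 0.

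**Precision if the MMQ were repeated (illustration only).** The 95% half-width for a two-arm mean difference, in SD units, is t(0.975, 2n-2) x sqrt(2/n). With n = 30 per arm, 2.002 x 0.258 = 0.52 SD. With n = 24 per arm (20% attrition, an assumption, since the document gives no rate), 2.013 x 0.289 = 0.58 SD. This shows what the added forms would buy. It does not measure the defect.

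**The case against.** The strongest reply is that no contradiction is proved. The plan never says the MMQ is the motivation measure; that is inferred from its title.

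There is also circumstantial evidence that baseline-only was deliberate. The schedule was reworked between the beta and RCT tables: the CUDIT and PHQ-8 gained follow-ups, the GAD-7, BASIS-R and Cannabis Expectancy Questionnaire were dropped, and Morningness/Eveningness and the Working Alliance Inventory were added. The MMQ stayed as it was, next to another baseline-only descriptor. The construct in Data Analysis is specific to sleep, and by title the Substance Use Sleep Scale fits that at least as well as a general motives questionnaire. The daily surveys, which the beta-phase text says also cover cannabis use, and the reasons for cannabis use listed under Data Collection might carry related items too. On this reading one clarifying sentence is enough, and the analysis is exploratory in any case, since the plan concedes that the sample cannot support formal mediation.

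Part of this stands. It cannot be said that motivation goes unmeasured at follow-up, and the count of lost forms holds only if the MMQ was meant. But none of the alternatives is shown to measure motivation, and the plan selects none of them. A reader who prefers the Substance Use Sleep Scale still reaches the conclusion that the plan must name it. That instruments go unassigned for the other mechanisms too is a weaker defence, because their titles or the plan's own examples make the match evident and they are repeated.

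**Conclusion.** The concern holds and should be fixed. Two facts are firm: the MMQ is scheduled at baseline only, and no repeated instrument is designated for cannabis-use motivation although follow-up and change analyses of it are promised. The loss of follow-up data is conditional on the MMQ being the intended measure, which the document neither confirms nor excludes. The other branch leaves an unspecified measure and costs no data.

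The reach is limited to part of Aim 2(c). The other three mechanisms have repeated instruments, and the primary insomnia outcome and the feasibility objectives are untouched. It is worth acting on because follow-up forms that are never given cannot be recovered at analysis.

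**What to change.** Choose one course and state it.

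1. **If the MMQ is the motivation measure:** mark it at the ~8-week and ~16-week follow-ups in the RCT table, and add it to both follow-up surveys. This is one existing form per visit, taking the marked rows from 22 to 23 at ~8 weeks and from 19 to 20 at ~16 weeks. It lengthens the surveys slightly and needs a minor amendment. Participants already past a follow-up would lack the data for that visit, and the report should say so.
2. **If a repeated instrument was meant** (for example the Substance Use Sleep Scale or Perceived Relief): name it and the score to be used in the Aim 2 Data Analysis section, and describe the MMQ as a baseline characteristic only. This is a text change with no added data collection. It should be made before outcome data by arm are examined.

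Under either course, one sentence in Data Analysis assigning an instrument to each of the four mechanisms would remove the ambiguity.

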Specimens: In this study, we will be collecting urine to analyze for recent cannabis and other illicit drug use. The urine drug screen will provide information regarding recent use for opioids, cannabis, amphetamines, methamphetamines, and cocaine. We will be using urine testing kits that give immediate results; therefore, the study staff will be conducting the sample testing and no labeling or storage will be necessary. Participants will be given a small bag containing the test kit to take into a restroom, either at the recruitment/follow up location or at home, or they will be mailed a urine drug screen to use at home. Once the specimen has been provided in the test cup, the participant will either return the bag to the research staff member for immediate testing or schedule an appointment with research staff using a video chat platform (BlueJeans, Skype for Business, or Zoom through the University of Michigan) to use the urine drug screen off camera and immediately share the results with research staff. A final option is for participants to send a picture of the results to the secure study email. Research staff will record test results. After testing is complete, the urine sample will be discarded by flushing it down the toilet if done in person. No identifying information will be marked on the testing container. The validity of self-report of cannabis use and other illicit drug use may be increased when a urine drug screen is performed. Specimens will be collected in a specimen container about 4 oz. in size, although only a minimal amount of urine is needed.

Assessment Instruments	Screening/ Eligibility	Baseline	Before and/or after session	Follow Up ~8 weeks	Follow Up ~16 weeks
Demographics	X				
Alcohol, Smoking and Substance Involvement Screening Test (ASSIST)	X				
Fagerstrom Test (for nicotine dependence)	X				
Fagerstrom Test (for cannabis dependence)	X				
Cannabis Use Disorder Identification Test (CUDIT)	X			X	X
Perceived Relief (PR)	X			X	X
STOP-BANG (Obstructive Sleep Apnea measure)	X				
Restless Leg Syndrome Questionnaire (RLSQ)	X				
Insomnia Severity Index (ISI)	X			X	X
Morningness/Eveningness Questionnaire		X			

Urine Drug Screen	X			X	X
Personal Health Questionnaire Depression Scale (PHQ-8)		X		X	X
12-Item Short Form Health Survey (SF-12)		X		X	X
Timeline Follow Back		X		X	X
Modified Self Efficacy Scale (SES)		X		X	X
Dysfunctional Beliefs About Sleep (DBAS-16)		X		X	X
Substance Use Sleep Scale (SUSS)		X		X	X

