Informed consent. A two-level consent procedure will be used in this study. At screening and baseline, participants will be asked to provide informed consent. After screening, those eligible will be asked to complete a second consent. To enhance confidentiality and minimize the collection of identifying information about individuals who do not participate in the study, screening consent will be administered online (a waiver of documentation of informed consent for screening is requested) or on study provided tablet computers as the first page of the screening survey. Prospective participants that use the online screening process will enter the survey portal from a link provided in the recruitment ad (paper or electronic) directing them to the UMHealthResearch.org site, where a link for the survey will be available. After clicking the survey link, they will then be asked to review and sign an e-consent to the short screening survey. During initiation of the screening survey each participant will be assigned a unique respondent ID number by REDCap. Participants will give consent by checking a box on the electronic consent form and will self-administer a screening survey. In the event of technological issues with study tablets or internet service, or participant preference, verbal consent may be obtained for screening and paper/pencil surveys completed. Following determination of eligibility, negative screens will receive a thank you page asking for a phone number or email address to be sent their gift card and ending their participation. The only identifying information collected from those who complete the screen and are ineligible or choose not to participate in the study will be an email address or phone number, to text or email Amazon gift card codes for screening assessment remuneration. Eligible participants will be asked to provide their name, email address, and phone number for scheduling purposes. Study staff will reach out to eligible participants to schedule the urine drug screen and baseline assessment.

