For those eligible based on screening responses and interested in participating in the full study, written or verbal informed consent for the full study will be obtained. Individuals interested in participating in the study will review the consent that will be emailed, texted or handed to them with the research staff in person or via a video chat platform (BlueJeans, Skype for Business, or Zoom through the University of Michigan). All participants will be told that participation is voluntary, that they can withdraw at any time, and that this will not impact any aspect of the services they receive at the clinics or dispensaries, including their ability to receive cannabis (if recruited from dispensaries). After reviewing the consent form, research staff will ask the patient if he/she has any questions regarding their participation or the study requirements and limitations. The limits of the Certificate of Confidentiality are explained in the consent form, but study staff will also verbally explain the limits of confidentiality. Any patients who request more time to review the consent form or consult with others will have the opportunity to do so. These patients will have the opportunity to have research staff contact them at a later time or to contact research staff themselves. Those interested in participating will be asked to consent to the research project. When providing informed consent, participants will be given, mailed or emailed a copy of the consent form to keep and the original will be filed in a confidential research file or study staff will record the date, time, and research staff conducting the consent in the secure database. Study staff will review the consent form for accuracy and completeness before beginning any study procedures. RAs will fully review the consent document, answer all questions and provide a copy of the consent document to the participant. All consent information will be filed in a confidential research database.

Study Eligibility Criteria.

Inclusion criteria. (1) age > 21 or older; (2) Insomnia Severity Index (ISI) score >10, indicative of at least “mild” insomnia; (3) use of cannabis three times a week within the past three months; (4) self-reported use of cannabis to manage insomnia at least once a week over the past month; (5) consistent access to a telephone, smartphone, laptop, or tablet; and (6) a positive urine drug screen for THC.

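### The RCT's primary outcome is change from baseline ISI, but no ISI is scheduled at baseline; if the screening score that decided entry fills the gap, within-arm change is inflated and the baseline SD is too small

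*Combined protocol and SAP*

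**What the plan says.** The Primary outcomes paragraph for the RCT (Human Subjects Considerations, Specific Aim 2) defines the insomnia outcome as a change score: "This will be measured by the change from baseline Insomnia Severity Index score to the score at study completion".

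The RCT table of assessment instruments gives the ISI three marks, "Insomnia Severity Index (ISI) X X X". They fall under screening/eligibility, the 8-week follow-up and the 16-week follow-up. The baseline cell is blank. The SF-12 also has three marks, "12-Item Short Form Health Survey (SF-12) X X X", but its first is under baseline, as it is for the PHQ-8, Timeline Follow Back and DBAS-16. The table thus treats screening and baseline as different occasions.

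The RCT inclusion criteria select on the same instrument: "Insomnia Severity Index (ISI) score >10, indicative of at least “mild” insomnia". For people screened online, baseline comes later, after an interval that is not stated: "Study staff will reach out to eligible participants to schedule the urine drug screen and baseline assessment".

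Data Analysis under Specific Aim 2 says that "we will calculate means and standard deviations for primary and mechanistic measures at baseline, post-treatment, and follow-up", together with change scores in each arm. Group comparisons are by t-test. Confidence intervals for between-group differences are named as the focus.

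**The concern.** A change score needs a defined starting value, and the schedule supplies none apart from the score that decided entry. People admitted because they scored above a threshold on one occasion will, on average, score lower next time even if nothing has changed, because some were above it through a transient high. If the admitting score is also the baseline, that drop is counted as improvement. The admitted scores are also cut off from below, so their SD is smaller than that of a second measurement in the same people.

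This matters more in a pilot than in a confirmatory trial. The plan names the within-arm distribution of the outcomes as one of the things it will estimate, to help design a later, fully powered trial. A spurious fall in the sleep education arm could be read as control-group response, and in the CBTi-CB arm as part of the response to therapy.

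**Working it through.** The plan gives no ISI mean, SD, repeatability or power calculation, so there is no figure of its own to reproduce. The check is of size only.

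**Input from the documents.** Entry requires ISI above 10, that is 11 or more on an integer scale, so the cut is set at 10.5.

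**Assumed inputs (not in the documents).** Among people screened: mean μ from 10 to 16 and SD σ from 4 to 6. Correlation ρ between any two occasions: 0.7 to 0.9, the same for every pair. Scores approximately normal, no treatment effect.

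**Formulas.** Let a = (10.5 − μ)/σ, λ = φ(a)/(1 − Φ(a)) and k = 1 + aλ − λ².

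- Spurious mean fall from the screening score: (1 − ρ)σλ
- Variance of the screening score among those admitted: kσ²
- Variance of a separate baseline score in the same people: ρ²kσ² + (1 − ρ²)σ²
- Variance of change from the screening score: (1 − ρ)²kσ² + (1 − ρ²)σ²
- Variance of change from a separate baseline: 2(1 − ρ)σ²

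**Middle case: μ = 12, σ = 5, ρ = 0.7.**

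- a = (10.5 − 12)/5 = −0.30; λ = 0.617; k = 1 − 0.185 − 0.381 = 0.434
- Spurious fall = 0.3 × 5 × 0.617 = 0.93 points
- Baseline SD, screening score: √(0.434 × 25) = 3.29
- Baseline SD, separate score: √(0.49 × 10.85 + 0.51 × 25) = √18.07 = 4.25, so the screening SD is about 23% smaller
- Change SD from screening: √(0.09 × 10.85 + 12.75) = √13.73 = 3.70
- Change SD from a separate baseline: √15 = 3.87, so the first is about 4% smaller

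**Ends of the assumed range.**

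| μ, σ, ρ | Spurious fall (points) | Baseline SD, screening vs separate | Change SD, screening vs separate |
|---|---|---|---|
| 16, 4, 0.9 | 0.07 | 3.44 vs 3.55 (3% smaller) | 1.78 vs 1.79 (0.7% smaller) |
| 12, 5, 0.7 | 0.93 | 3.29 vs 4.25 (23% smaller) | 3.70 vs 3.87 (4% smaller) |
| 10, 6, 0.7 | 1.53 | 3.53 vs 4.95 (29% smaller) | 4.41 vs 4.65 (5% smaller) |

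Lowering ρ to 0.6 extends the worst case to 2.04 points, 33% and 7%.

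**Simulation of the middle case.** Integer scores were bounded at 0 and 28 (an assumed range), with 30 per arm and no effect. The mean change was −0.94 from the screening score and 0.00 from a separate baseline. The between-arm difference in change averaged 0.00, and the two-sample t-test rejected in 4.9% of trials. A paired test within one arm, which the plan does not propose and which is used here only as a yardstick, gave p < 0.05 in 27% of trials.

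**The case against.** The strongest reply is that nothing in the plan says the screening score is the baseline. The overview of Specific Aim 2 speaks of self-reported insomnia assessment before treatment. The Recruitment Procedures and Data Collection paragraphs for the RCT say the baseline visit gathers sleep data. This stands as a limit: use of the screening score is an inference from the schedule. But none of that text names the ISI at baseline, and the diary, Epworth scale and DBAS-16, which are scheduled there, would satisfy it.

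The blank cell may also be deliberate. The CUDIT, Perceived Relief and the urine screen are likewise taken once before treatment, at screening, and repeated at follow-up. That is a reasonable way to limit burden, but the plan would then need to say that the screening ISI is the baseline and accept the consequence for within-arm change.

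Three stronger readings are tempting, and the documents do not support them.

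- *The treatment comparison is biased.* It is not. The artefact is the same in both arms, and the between-group intervals that Data Analysis puts first are unaffected.
- *The variability of the primary outcome is seriously distorted.* The outcome is a change score, whose SD moves by only about 1 to 5%. The standard error of an SD from 30 people is about 1/√58 = 13%, so this shift is lost in sampling noise. If the later trial used the same screening-based change score, this SD would even be the relevant one for planning. The larger shrinkage applies to the baseline ISI SD alone.
- *A truncated score weakens covariate adjustment.* The plan uses t-tests and describes no adjustment for baseline ISI.

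It is also fair that the size rests wholly on assumed inputs and spans about twentyfold. If most people screened score well above 10, or the ISI is highly repeatable, the effect is negligible.

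**Conclusion.** The gap is real: the primary outcome is change from baseline, and the only ISI scheduled before treatment is the one tested against the entry threshold. If that score is used as the baseline, within-arm ISI improvement is overstated in both arms by about 0.07 to 1.5 points, and the baseline ISI SD is understated by 3 to 29%. Both ranges depend on the assumed mean, SD and correlation. The problem is confined to the ISI among the main measures; the SF-12, Timeline Follow Back and DBAS-16 have their own baseline marks. This is a worthwhile, inexpensive improvement to within-arm quantities that the pilot sets out to report, and not a threat to the validity of the randomised comparison.

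**What to change.** Mark the ISI in the baseline column of the RCT table and place it in the existing baseline survey, which is completed before randomisation. Name that score as the starting value for the primary change score and as the source of the baseline mean and SD. Keep the screening ISI for eligibility only.

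State explicitly that the cut-off of 10 is not re-applied to the baseline ISI. The RCT Data Collection paragraph says baseline assessments confirm eligibility; if the threshold were used again there, the selection effect would return.

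The cost is one short questionnaire repeated once per participant and a schedule amendment. The benefit is limited where screening and baseline fall in the same session, because a near-immediate repeat shares the same transient error and removes little regression to the mean. The interval between the two should therefore be recorded. Where only a screening score exists, report it as the baseline and present within-arm change and the baseline SD with that limitation.
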